9.2 Handling

9.2.1 Encapsulation, Packaging, and Labeling

IP will be compounded, encapsulated, packaged, labeled, and shipped to sites by Zeeh Pharmaceutical Experiment Station, a Schedule 1-licensed Analytical Laboratory at the University of Wisconsin at Madison. IP in bulk will be sent from a Schedule 1-licensed Distributor to the Zeeh Station. Zeeh Station will provide bulk lactose for compounding. IP will be compounded with lactose (calculated as the weight of the hydrochloride salt) and placed in hydroxypropyl methylcellulose (HPMC) capsules.

Initial and supplemental dose IP for each Experimental Session will be stored in individual inner envelopes. Inner envelopes for initial and supplemental doses will be placed within each primary container. There will be one primary container per participant per Experimental Session. The IP for each Experimental Session will be packaged in one primary container, labeled with a unique container number, protocol number, IP name, lot number, sponsor name, IND number, Experimental Session number and a statement that the IP is restricted to clinical trial use only. All labels will comply with local, state, and federal regulations.

9.2.2 Accountability

Forms will be provided to track IP accountability and administration throughout the study. Openlabel IP accountability and administration logs will be reviewed during routine monitoring visits. IP will be handled in accordance with all local, state, and federal regulations and forms pertaining to the use of controlled substances, and forms will be maintained by the appropriate controlled substance license holder or delegate.

Each primary container label will contain a unique container number for the IP assigned to a single Experimental Session. The container numbers will be used to track IP administration in the Source Record and the IP administration log.

9.2.3 Storage

MDMA is a controlled substance and will be stored and handled in compliance with all relevant federal and state regulations. In accordance with these requirements, the appropriate license

holder or designee will be responsible for storing, dispensing, and administering the MDMA. It will be stored securely in accordance with federal, state, and local regulations.

9.2.4 Administration

IP will only be removed for a single Experimental Session at a time and will be administered orally at the study site. All doses administered will be recorded on the appropriate accountability and administration logs. Only the initial dose is required to be given at each Experimental Session. Supplemental doses should be administered unless contraindicated. Each dose (initial and supplemental) will be administered with a glass of electrolyte-containing fluid.

A person at the site authorized to manage and administer controlled substances will dispense the appropriate container for each Experimental Session. If a supplemental dose is not administered, the unused IP will be kept for accountability.

Records pertaining to the use of scheduled, regulated compounds will be maintained in accordance with relevant federal and state regulations.

9.2.5 Treatment Compliance

Compliance to protocol required doses will be guaranteed by the person licensed to manage and administer controlled substances for Experimental Sessions at each site. All administered doses will be recorded for IP accountability. The IP will be stored securely per regulations.

9.3 Participant Numbering

Every potential participant who is prescreened by telephone according to the IRB-approved script will be assigned a seven-character alphanumeric Screening Number and recorded on the Screening Log. This number will begin with 'S6' to identify that it is a Screening Number. The next two digits represent the site number (e.g., '11'), followed by a three-digit screening identifier starting with '601'. The screening identifier will be assigned to each prescreened participant at a site sequentially. For example, the first Screening Number at Site 11 will be S611601 and first Screening Number at Site 12 will be S612601.

Each participant who passes Screening and is enrolled in the trial at Visit 0 will be assigned a seven-digit Subject Number. The first digits will be '16'. The next two digits represent the site number (e.g., '12'), followed by a three-digit participant identifier starting with '001'. The participant identifier will be assigned to each enrolled participant at a site sequentially. For example, the first Subject Number at Site 12 will be 1612001.

Eligible participants will be enrolled in the study and sequentially assigned an identification number. All participants will also be assigned a unique participant identifier within the database for use in analysis.

9.4 Blinding and Bias Minimization

Eligibility will be determined by review of screening by the PI, site team and as needed the sponsor Medical Monitor prior to enrollment confirmation. Participants, site staff, and the sponsor will be aware that each participant in MP16 will be receiving open-label MDMA.

To further minimize bias in measuring effect, the sponsor will use an observer-blind, centralized, reliable IR pool to administer the Primary Outcome measure via live video interviews. The IR

Pool will have no knowledge of AEs and will only evaluate participants at Baseline and at the assessments scheduled after each Experimental Session. The IR Pool is blinded to study design, visit number, number of treatments, and any data from the treating therapy team after Baseline. IRs will be assigned to participants based on availability. Data will be entered by the IR Coordinator who is not part of the study assessments or procedures. Timing of CAPS-5 assessments are pre-specified in the study protocol within visit windows.

To ensure that all participants are treated in a similar manner, the sites will be required to follow the protocol and Treatment Manual delineating minimum length of time per visit type and describing delivery of treatment. All Experimental Sessions are required to be at least 8 hours long. Adherence to the Treatment Manual will be checked by review of video by adherence raters. The sponsor will monitor data in real-time to ensure complete data collection for all participants, including those who discontinue treatment. Sites will be required to make and document a specific number of attempts to obtain follow-up data per protocol. All participants who receive at least one dose of IP and complete at least one follow-up assessment will be included in the final mITT primary effect analysis.

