5.3.4 Early Termination from the Study

Participants who are removed from the study after they are enrolled and receive IP but do not complete the study may fall into one of these categories: Post-Dosing Early Termination or Dropout. If the participant has received IP in at least one Experimental Session and completed one CAPS-5 assessment beyond Baseline, they will be considered evaluable. All participants who receive IP in at least one Experimental Session will be included in all safety analyses.

Participants can withdraw from treatment or withdraw consent at any time for any reason without judgment. The site team can withdraw a participant if, in their clinical judgment, it is in the best interest of the participant or if the participant cannot comply with elements of the protocol that are critical for safety or for the scientific integrity of the study. If the site team makes the decision to terminate the participant from treatment or the study, they will explain the reason for withdrawal and document in the participant's source records and eCRF. If a participant develops any Exclusion Criteria that, in the opinion of the Medical Monitor or Site, affects the safety of the participant, including psychiatric diagnosis, pregnancy, or requiring use of prohibited medications, the participant will discontinue treatment in Experimental Sessions but remain in the study for the associated Integrative Sessions. Any time a participant terminates from the study early, the site team will attempt to obtain information about AE outcomes if appropriate, as determined by the site physician and Medical Monitor. The site team will provide the participant with an Exit Plan as described in Section 8.4.3.2 Exit Plan.

 Post-Dosing Early Termination: Participants who discontinue study treatment but continue to participate in study evaluations and outcome assessments. Data collection by IRs will continue on the same schedule as planned through Study Termination visit procedures.

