5.3.5 Lost to Follow-up

A participant will be considered lost to follow-up if they fail to attend scheduled visits and are unable to be contacted by the site staff. If the participant has completed at least one Experimental Session and one CAPS-5 assessment beyond Baseline, they will be considered evaluable. All participants with at least one Experimental Session will be included in the safety analysis.

If a participant does not attend a scheduled visit, the site must attempt to contact the participant to reschedule the visit as soon as possible and emphasize the importance of complying with the protocol specified visit schedule. The staff should determine if the participant is willing to comply with future visits.

If a participant does not respond to this initial contact, the site staff must make multiple efforts to contact the study participant and document each attempt in the source record. At least three attempts should be made via telephone, over the course of approximately 1 week, with calls at different times of day. If telephone contact fails, an email should be sent if such contact information was provided. The emergency contact the participant provided should be contacted. and attempt contact with their support person. Lastly, a certified letter (or equivalent) should be sent to their last known mailing address. If the participant fails to respond to all of these contacts, they will be considered to have withdrawn from the study and are lost to follow-up.

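### Under Protocol 5.3.5 a fully dosed participant who goes silent after V15 can be closed out before the V19 window opens, and no renewed attempt at the primary outcome is required

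*Protocol*

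**What the plan says.** Protocol 9.4 names two safeguards for follow-up data. One is a duty on sites: "Sites will be required to make and document a specific number of attempts to obtain follow-up data per protocol". The other is oversight: "The sponsor will monitor data in real-time to ensure complete data collection for all participants, including those who discontinue treatment". Section 9.4 itself gives no number of attempts and names no visit.

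The numbered attempts are in Protocol 5.3.5:
- **Trigger and aim.** "If a participant does not attend a scheduled visit, the site must attempt to contact the participant to reschedule the visit as soon as possible".
- **Calls.** "At least three attempts should be made via telephone, over the course of approximately 1 week". An email and the emergency contact follow.
- **Last step.** "a certified letter (or equivalent) should be sent to their last known mailing address". No waiting time is given.
- **End point.** "If the participant fails to respond to all of these contacts, they will be considered to have withdrawn from the study".

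Other participants who leave treatment or the study have a stated route to a final CAPS-5:
- Those who stop treatment but stay in the study (5.3.4): "Data collection by IRs will continue on the same schedule as planned through Study Termination visit procedures".
- Those who withdraw consent complete a final CAPS-5 if they agree (5.3.4).
- Those withdrawn from treatment have one at once (8.4.2).
- In pregnancy, efforts are to be made to obtain one (11.3.3).

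V19 is a telemedicine interview by the central rater pool (Table 1; 8.4.2).

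**The concern.** The attempts that 9.4 relies on follow the missed visit, not the outcome. If they fail, silence is recorded as withdrawal from the study, even though the participant never withdrew consent. Nothing then tells the site to try again when V19 falls due. After V18 there is no scheduled visit until V19 (8.4.1), so for someone already closed no later event restarts contact.

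The primary outcome is at stake. A participant who has had all three Experimental Sessions and has a V8 or V13 assessment stays in the mITT set but has no V19 value. The MMRM then relies on that value being missing at random, which is least secure for people who go silent. SAP 8.7.1 does not impute, SAP 8.2 does not replace participants, and the Per Protocol set requires three follow-up CAPS-5 assessments (Protocol 14.1; SAP 8.1). The study is also meant to check assumptions behind the Phase 3 power calculations, so recoverable V19 values matter to a stated purpose.

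**Working it through.** The plan states no figure for this point, so there is none to reproduce. The check is a timeline and a reading of the analysis rules.

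**1. Inputs**

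| Input | Value | Source |
|---|---|---|
| V17 | about 2 weeks after V15 | Protocol 8.3.3, Table 1 |
| Calls | at least 3 over about 1 week | Protocol 5.3.5 |
| Wait after the letter | not stated; assumed 0, 1 or 2 weeks | assumption |
| V19 | 8 (+/-2) weeks after V15 and 18 (+/-3) weeks after Baseline | Protocol Table 1, 8.4.2 |
| Session spacing | V5 within 1 week of V3; sessions 3 to 5 weeks apart | Protocol 8.3.1 |
| Maximum N | 60 | Protocol 5.1 |

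**2. Closure of a non-responder after a missed V17**

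Closure (weeks after V15) = 2 + 1 + letter wait. By the V15 rule, V19 opens at 8 - 2 = 6, has its target at 8 and closes at 8 + 2 = 10.

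| Letter wait | Closure | Before opening | Before target | Before closing |
|---|---|---|---|---|
| 0 weeks | week 3 | 3 weeks | 5 weeks | 7 weeks |
| 1 week | week 4 | 2 weeks | 4 weeks | 6 weeks |
| 2 weeks | week 5 | 1 week | 3 weeks | 5 weeks |

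**3. When the V19 window opens**

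Both timing rules apply, so it opens at the later of 18 - 3 = 15 weeks after Baseline and V15 + 6 weeks.
- Latest permitted spacing: V15 at 1 + 5 + 5 = week 11, so the window opens at 11 + 6 = week 17.
- Nominal spacing: V15 at 1 + 4 + 4 = week 9, so both rules give week 15.
- Shortest spacing: V15 at 0 + 3 + 3 = week 6. V15 + 6 gives week 12, so the 15-week rule governs. Closure is at weeks 9 to 11, and the gap to opening grows to 4 to 6 weeks.

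The 1 to 3 weeks in step 2 is therefore the gap when the V15 rule governs. It is longer when the Baseline rule does.

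**4. Would the recovered value count?**

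SAP 8.7.1 excludes CAPS-5 data only after treatment discontinuation. Protocol 14.1.1.1 frames the de jure estimand around three Experimental Sessions, and 5.3.4 speaks of discontinuing treatment in those sessions while Integrative Sessions go on. On that reading, someone dosed three times has not discontinued treatment, and the V19 value belongs in the primary MMRM. For a participant lost before Session 3, V19 would follow discontinuation and would serve only the supportive de facto analysis (SAP 8.2).

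**5. How many?**

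SAP 8.2 expects up to 5% early termination: 0.05 x 60 = 3. The Phase 2 dropout rate in Protocol 2.2.4 is 8/107 = 7.5%: 8/107 x 60 = 4.5, so 4 to 5. Neither is split by cause or timing.

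**The case against.** The strongest reply is that the protocol is less harsh than it may look, and much of this stands.

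- **A reader might infer that missing V17 closes a participant out.** It does not. The site must first try to rebook, and withdrawal follows only if every call, email, emergency contact and letter goes unanswered. Someone who responds stays due for V19.
- **A reader might infer that V19 can never be offered after closure.** Nothing forbids it, and the monitoring sentence in 9.4 points towards complete data. V19 is itself a scheduled visit, so missing it triggers the full sequence for anyone still open. What remains is that no step is required for someone already closed.
- **Silence from V16 is unlikely in the main study.** V16 is held the morning after the overnight stay, and four calls follow in the first week. The realistic case starts at V17 or later.
- **Inclusion in the de jure analysis is not settled.** Protocol 8.3 describes each treatment as the Experimental Session plus its calls and Integrative Sessions, so someone gone before V17 could be said not to have completed Treatment 3. The reading in step 4 is the more natural one, but the documents do not state it.
- **The stakes are limited.** This is a single-arm, open-label study with no power calculation (SAP 7.0).

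These points narrow the concern. They do not supply the missing step.

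**Conclusion.** The concern holds in limited form. The contact rule that 9.4 depends on can end, for a fully dosed participant who misses V17 and answers nothing, about 1 to 3 weeks before the V19 window opens. No renewed attempt at the primary outcome is then required, although other leavers have a route to a final CAPS-5. The timing rests on V17 at week 2, about one week of calls and an assumed letter wait of 0 to 2 weeks.

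The number affected cannot be derived. The 3 to 5 of 60 is an upper illustration from all-cause rates. A reader might take it as the number recoverable, but it has no split by cause, and this protocol uses dropout for people who withdraw consent, whom a remedy must leave alone. A reader might also turn it into a bias in mean CAPS-5 change. That needs a deviation from the model's prediction that the documents do not give, so no bias figure should be stated. Nor does early loss, such as after a missed V7, strengthen the case for the primary analysis, because a later V19 would fall after treatment discontinuation.

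It is a cheap improvement worth making, not a flaw that undermines the study.

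**What to change.** In Protocol 5.3.5, with a cross-reference in 9.4, state that:

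1. A participant who has not withdrawn consent stays open for outcome collection after unanswered contacts.
2. Site staff make and document a renewed set of contact attempts when that participant's V19 window opens. This is the later of 15 weeks after Baseline and 6 weeks after V15, or 15 weeks after Baseline if V15 did not occur.
3. The V19 CAPS-5/SDS interview is offered even if site visits were missed.
4. Lost-to-follow-up status is assigned only if V19 is also not obtained.

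The task belongs with site staff because 9.4 places the IR Coordinator outside study assessments and procedures. The change affects no treatment and uses an interview already planned. It costs a few extra calls and a later final disposition for these participants, and not all of them will be recovered.

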10.0 Risks

10.1 Non-drug Related Risks

10.1.1 Medical Assessments

In preparation for MDMA-assisted psychotherapy sessions, blood draws and a full medical examination, including a physical examination, ECG, 1-minute rhythm strip, and laboratory tests, are required to establish eligibility for the study. Temporary discomfort, inflammation, or infection could arise as a result of sampling blood at the punctured vein. Submitting to a full medical examination may also cause discomfort or psychological distress. Since medical examinations and blood draws are required to establish eligibility for the study, they cannot be omitted from the protocol.

10.1.2 PTSD, Suicide Risk, and Psychotherapy

During Screening, throughout MDMA-assisted psychotherapy, and during assessment of study measures, participants will be asked to think about and discuss their thoughts and emotions relating to the traumatic event or events. They may experience intense emotional responses or suicidal ideation as a result of recalling and speaking about this material. Even in a therapeutic context, thinking about and discussing the trauma, symptoms related to the trauma or the effects of PTSD on life function can produce distress and exacerbate suicidal ideation during and immediately after psychotherapy sessions. Psychotherapy is conducted as part of this study, and people undergoing psychotherapy are expected to confront unpleasant thoughts, feelings and memories in the process. Because psychotherapy is an integral part of the research study design, the potential distress arising from psychotherapy is unavoidable. Therapy teams will provide emotional support to participants during any psychological distress.

The therapy team will minimize risks by carefully evaluating all participants to determine if there is a current risk of suicidal behavior. Participants with a history of suicide attempts will not be excluded unless significant risk of suicidal behavior is present at the time of Screening. Participants will be enrolled according to the Eligibility Criteria based on the clinical judgment of the site physician, therapy team, and Medical Monitor.

A qualified individual will administer the C-SSRS according to Table 6: Time and Events – Study Measures, and as needed depending on clinical presentation of the participants, to monitor for development and intensity of suicidal ideation and/or behavior. The therapy team will implement the following plan to assess elevated or imminent suicide risk.

If the Since Last Visit C-SSRS reveals current serious Suicidal Ideation (scores of four or greater), indicating risk at the time of the assessment, or positive Suicidal Behavior (scores of one or greater), the participant will be referred for further management as described below.

- 1. If the participant has current suicidal ideation, but no specific plan to commit suicide (Suicidal Ideation Score=4), the individual administering the C-SSRS will ensure:
 - a. The participant is evaluated by the investigator and/or site physician to determine an appropriate course of action. Findings will be discussed with the participant and their personal therapist, if applicable.
 - b. Regular check-ins via phone or in-person will be continued until the participant has stabilized or a new course of action is taken based on changes in C-SSRS score and/or ongoing clinical assessment.
 - c. Increases in suicidality will be captured as an AE.
 - d. Treatment would be continued when deemed appropriate by the investigator and Medical Monitor, unless it is determined that treatment should be discontinued, in which case the participant will enter follow-up.
- 2. If the participant has suicidal ideation, and a plan to commit suicide (Suicidal Ideation Score=5) or positive Suicidal Behavior (Score greater than or equal to 1), the individual administering the C-SSRS will assess whether the risk is imminent. A Suicidal Ideation score of five does not necessarily indicate an immediate risk if the thoughts are fleeting, fairly easily controlled, and deterrents are strong. If there is no imminent risk, the individual will follow the procedure described above. If there is imminent risk of suicidal behavior, the individual will ensure:
 - a. Participants are evaluated by the investigator or site physician to determine an appropriate course of action, and the therapy team will contact their personal therapist, who will be invited to come to the study site to assist, depending on their location.
 - b. If it is determined that the participant is at imminent risk of suicide, the therapy team will do one of the following:
 - i. Escort the participant to the ED;
 - ii. Escort the participant to an appropriate mental health services facility (e.g., hospital psychiatric unit); or
 - iii. Call EMS and ensure that the participant is transferred to the responding medical personnel.
 - c. If the participant will not comply and wishes to leave without consultation, call EMS. Explain that the participant is in immediate danger of committing suicide. Provide a complete description of the participant and give any other needed details to ensure the participant's safety.
 - d. Notify appropriate members of the study team and sponsor representatives.
 - e. The event will be collected as an AE and the seriousness will be evaluated. SAEs will be reported per FDA guidance.
 - f. Treatment would be continued when deemed appropriate by the investigator and Medical Monitor, unless it is determined that treatment should be discontinued, in which case the participant will enter follow-up.

